1. OBJECTIVES

2.1 Primary Objective

To establish patient and public views on the sharing of identified health data (for clinical purposes) and de-identified health data (for research) within the UK.

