2.1 Study Participants

Study participants will be members of the public from the UK who wish to take part in the online survey

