c) One method of recruitment will be via the Cambridgeshire & Peterborough NHS Foundation Trust (CPFT) Research Database (ethics ref. 17/EE/0442), which contains linked anonymous information derived from CPFT clinical records. The database will be queried to find patients that are likely to meet the study's eligibility criteria, yielding a list of research identification numbers. This list will be submitted to the CPFT Research Database Manager, who will enter them into an automated system that can identify the patients. For patients that consent (either having previously consented, or having given specific consent after being approached by their primary clinical team), and only those patients, the Research Database Manager will provide the patient's details to the research team, and authorize them to view the patient's CPFT clinical records and to contact the patient to discuss participation in the study. Study participation itself, or provision of any additional information, would require the patient's further consent. (The ethics-approved consent process for this system includes consent for researchers to see medical information, but for the present study, no medical details would be accessed.)

d) Similar approaches to enhance participation may be used in other participating NHS sites, where Trust approved 'Research contact' lists or methods to contact potential research participants have been established e.g. newsletters websites, social media

e) Approaching staff through approved Trust communications e.g. newsletters, websites social media, etc to offer participation.

Primary care/community care

a) Displaying the studies advertising literature (posters, leaflets etc.) in the primary/community care setting for potential participants to read/take home

b) Handing leaflets directly to potential participants using their services.

c) Search of GP records by those members of the direct care team with permission to do
 so

d) Using established service approved 'research contact' lists or methods to find potential research participants e.g. by newsletters, websites, social media

e) Approaching staff through approved communications e.g. newsletters, websites, social media etc to offer participation.

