- 30 PA Harris, R Taylor, R Thielke, J Payne, N Gonzalez, JG. Conde, Research electronic data capture (REDCap) A metadata-driven methodology and workflow process for providing translational research informatics support, J Biomed Inform. 2009 Apr;42(2):377-81.

10 Appendices

Appendix 3

Survey

The live survey can be found at:

https://www.redcap-ide-cam.org.uk/surveys/?s=NKTYE8JHCT

or accessed through the project team's website: https://www.climbproject.org.uk/

Actual Survey

Before starting we would like to know where you heard about our study. This is particularly important if you were given information by a GP practice, Hospital or other member of staff. You may prefer not to say if you wish.

• Prefer not to say

• GP (via a poster, leaflet, or from a staff member) [If ticked an option to include GP surgery name will appear]

• Hospital (via a poster, leaflet, or from a staff member) [If ticked an option to include a hospital trust will appear]

- Another health care professional
- Group to which I belong
- Charity website/email/newsletter etc.
- Social media
- Poster (other than at your GP or hospital)
- Browsing the internet
- Friend
- Not sure
- Other (Please specify)

Please read the following definitions:

- By "NHS" we mean all parts of the national health service in the UK: NHS England, NHS Scotland, NHS Wales, and Health and Social Care in Northern Ireland (HSC) and referred to as NHS in this survey
- Health data means any information about a person's health such as might be collected by a nurse, doctor or other appropriate member of NHS staff. Health data includes things like your medical notes, blood test results, prescription information, scans etc.
- Identifiable health data means any health data (as described above) that can also identify a person e.g. any health data that also contains names, addresses, NHS numbers etc.

• Clinical care means providing health care directly to people, for example, diagnosing illnesses or treating ill health

Q1.

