An NHS psychological therapy service, e.g. IAPT or other		
therapy service (ONLINE)		
NHS outpatient or community mental health services, or key		
worker		
NHS crisis care/Home Treatment teams		
NHS inpatient mental health services in a mental health		
hospital		
NHS inpatient mental health services in a general hospital		
(liaison psychiatry)		
Private services		
Services in the workplace e.g. Occupational Health		
Charity providing mental health support		
Online forum		
Other (Please specify)		
01	· ·	•

Q4

We are also interested to know if you have accessed any services regarding your own physical health. This could be services like your GP, outpatient hospital appointments, inpatient services, online support, Accident and Emergency, 111 service, private services, charities providing physical health support, etc.

Have you ever used any of the following services for your own physical health?

- I prefer not to say [Will take you straight to Q5]
- I have used physical health services (this includes using your GP)
- I have not used any physical health services [Will take you straight to Q5]

Q4a

And finally, in this section, we would like to know if you would be willing to share what physical health services you have used for your own physical health. You may tick as many boxes as you wish.

Please use the 'next page' button if you prefer not to answer.

Services used	Recently (in the	More than 5
	last 5 years)	years ago
Physical health support from your GP or surgery		
NHS hospital outpatient services (outpatient clinics etc.)		
NHS Urgent Care Centre (not A&E) or NHS 111 helpline		
NHS Accident and Emergency services (A&E)		
NHS inpatient services (procedures not completed in 1 day)		
NHS Day Surgery/day care in a hospital		
Private services		
Services in the workplace e.g. Occupational Health		

Charity providing mental health support	
Online forum	
Other (Please specify)	

Moving on...

The table below shows what NHS identifiable health data may look like. This sort of data is used for health care by NHS staff. (Please note the examples shown are not real).

NHS number	Title	Forename	Surname	Date of birth	Address	Diagnoses	Notes
9876543210	[name]	20 Jan 1950	1 The Street, Maidstone	pneumonia high blood pressure	1 Apr 2019. Seen in clinic. [name] has a fever and a cough. His chest sounds crackly. I think he has pneumonia. Sent to hospital.

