Do (did) you supervise any other employees on a day to day basis?

• Prefer not to say [If ticked will automatically move to question about where you live]

- Yes
- No

And which best describes the work you do (did)?

- Prefer not to say
- Modern professional occupations such as: teacher nurse physiotherapist social worker welfare officer artist musician police office (sergeant or above) software designer
- Clerical and intermediate occupations such as: secretary personal assistant clerical worker - office clerk - call centre agent - nursing auxiliary - nursery nurse
- Senior managers or administrators (responsible for planning, organising, and co-coordinating work and for finance) such as: finance manager chief executive
- Technical and craft occupations such as: motor mechanic fitter inspector plumber printer tool maker electrician gardener train driver
- Semi-routine manual and service occupations such as: postal worker machine operative security guard caretaker farm worker catering assistant receptionist sales assistant
- Routine manual and service occupations such as: HGV driver van driver cleaner porter packer sewing machinist messenger labourer waiter/waitress bar staff
- Middle or junior managers such as: office manager retail manager bank manager restaurant manager warehouse manager publican
- Traditional professional occupations such as: accountant solicitor medical practitioner scientist civil/mechanical engineer

And where in the UK do you currently live?

- Prefer not to say
- England
- Northern Ireland
- Scotland
- Wales
- Channel Islands
- Isle of Man
- None of these

[If England ticked the following further options appear:

Prefer not to say, North East, North West, Yorkshire and Humber, West Midlands East Midlands, East of England, London, South East, South West, Other (Please specify)]

[If Scotland ticked the following further options appear: Prefer not to say, North Scotland, North East Scotland, East Scotland, West Scotland, South Scotland, Other (Please specify)]

We would like to know your postcode so that we can analyse our results by "geography", such as urban versus rural areas. You do not have to give this. However, if you do, we will never disclose it or identify you from it.

- I prefer not to give my postcode
- I am happy to give my postcode [If ticked box provided to type in postcode]

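### Staff are recruited through work channels, but no survey item records health-service employment, so the descriptive results cannot be checked for an over-representation of staff

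*Protocol*

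**What the plan says.** **Who is to be described.** Section 2.1 (Primary Objective) reads: "To establish patient and public views on the sharing of identified health data". The Study Participants section adds: "Study participants will be members of the public from the UK who wish to take part in the online survey". Sections 3.2 and 3.3 require consent and UK residence, and exclude only those under 16 without permission from a parent or guardian.

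**How staff are reached.** Section 4.1, item (e) of the secondary care list: "Approaching staff through approved Trust communications e.g. newsletters, websites social media, etc to offer participation". Item (e) of the primary/community care list: "Approaching staff through approved communications e.g. newsletters, websites, social media etc to offer participation". Section 6.1 bases the expected 20,000 responses on sites that have expressed interest.

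**What the survey records (Appendix 3).**
- The source question asks where the respondent heard of the study. One option is "Hospital (via a poster, leaflet, or from a staff member" (with an optional trust name). No option covers an employer's communication.
- Q3b to Q4a concern services used for the respondent's own health, for example "We are also interested to know if you have accessed any services regarding your own physical health".
- The employment items cover employee status, employer size and supervision, but not who the employer is.
- One occupation class begins "Modern professional occupations such as: teacher nurse physiotherapist social worker" and continues with artists, musicians and software designers. Doctors share a class with solicitors and accountants, nursing auxiliaries with secretaries, and porters with van drivers.

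Section 6.3 lists the predictors to be examined. Employment in the health service is not among them.

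**The concern.** Primary measures (a)-(f) in section 6.3 are levels of support for sharing health data without explicit consent each time. Clinical and research staff are among the people who would use such data, and Appendix 3 itself says that the consent form would save health care professionals time. Their views may therefore differ from those of other respondents. Two Q15 items, on understanding who NHS-approved researchers are and on prior awareness of the National Data Opt-Out, could also reflect job knowledge.

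Staff are a recruitment target in their own right, so their share of the sample could exceed their share of the population. A larger sample does not reduce a shift of that kind. A separate analysis plan could not repair it either, because it cannot stratify, exclude or weight on a variable that the questionnaire does not collect.

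**Working it through.** **1. The plan's own figure.** Section 6.1 states n = 1,269 for three groups, f = 0.1 and power 0.9. It gives no alpha, so I take 0.05. With a noncentral F on 2 and N − 3 degrees of freedom and noncentrality N × f², the smallest N with power of at least 0.9 is 1,269 (423 per group, power 0.9001). The figure reproduces, and this point does not touch it.

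**2. Formula for the shift.** Let s be the staff share of the sample, π the staff share of the population, and d the staff minus non-staff difference in support. Taking each group's respondents as typical of that group, to isolate composition:
- sample value = non-staff support + s × d
- population value = non-staff support + π × d
- shift = (s − π) × d

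Staff belong to the target population, so only their excess share counts. The simpler product s × d would overstate the shift.

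**3. Inputs.** The documents give no value for s, π or d. Assumed ranges: π = 3-5%, s = 10-30%, and d = 10-20 percentage points in absolute size, either sign.

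**4. Size of the shift, in percentage points.**

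| s | π | d | (s − π) × d |
|---|---|---|---|
| 10% | 5% | 10 | 0.05 × 10 = 0.5 |
| 10% | 3% | 10 | 0.07 × 10 = 0.7 |
| 30% | 5% | 20 | 0.25 × 20 = 5.0 |
| 30% | 3% | 20 | 0.27 × 20 = 5.4 |

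**5. Comparison with nominal precision.** The 95% half-width under simple random sampling at p = 0.5 is:
- n = 20,000: 1.96 × √(0.25/20,000) = 0.69 points
- n = 1,269: 1.96 × √(0.25/1,269) = 2.75 points

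With d = 10, the shift equals the half-width when the excess share s − π is 0.69/10, about 7 percentage points, at n = 20,000, or 2.75/10, about 28 percentage points, at n = 1,269.

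**6. Can existing items stand in?** A named trust, free text under the source question's 'other' option, and occupational class allow a crude bound. They do not separate the groups. Dropping the class that contains nurses also drops teachers and musicians, and leaves in doctors, auxiliaries and porters.

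**The case against.** The strongest reply is that nothing contradicts the objective. NHS staff are UK residents, patients and members of the public. They meet the inclusion criteria, and the questions ask about their own data. That stands: a reader might infer that recruiting staff is a mistake, and the documents do not support this.

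A reader might also infer that staff inflate support for sharing. The documents report no staff attitudes. Section 1.2 does cite clinical dangers from restrictive sharing, but it attributes that restriction to fear of breaching information governance law, and section 1.4 likewise mentions fear of inappropriate disclosure. Staff could be the more cautious group.

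The half-widths are a flattering yardstick. This is an open, self-selected survey promoted through charities, media, contact lists and events, so many compositional imbalances could exceed 0.69 points, and staff are one among several. That also stands. What distinguishes staff is that the plan recruits them deliberately and by name, and that one question would make the imbalance visible.

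Finally, the predictor list in section 6.3 is open-ended and the proxies permit some bounding. Both are true, but an open list does not help when the variable is not collected.

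**Conclusion.** The point holds as a gap in what the survey records. Staff are deliberately recruited through both care settings, and no item identifies them, so the descriptive measures (a)-(f) and the two Q15 items cannot be checked against a possibly over-represented group with a working interest in the answer.

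Under the assumed ranges the shift is about 0.5 to 5.4 points, of unknown sign. At the low end it is at or below the nominal half-width for n = 20,000. At the high end it exceeds the half-width at either sample size. All three inputs are assumptions, so this is an illustration and not an estimate of bias.

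The randomised framing comparison keeps its internal validity, because staff should balance across the three statements.

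It would go too far to treat non-staff as the public. Under the same assumptions, a non-staff figure would itself miss the population value by π × d, from 0.03 × 10 = 0.3 to 0.05 × 20 = 1.0 points.

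**What to change.** 1. Add one item to the demographics at the end of Appendix 3: *Do you currently work for the NHS/HSC or in health research? Yes, with patients or patient records / Yes, other role / No / Prefer not to say.* Placed there, it follows the framing statements and Q5 to Q10 and cannot prime professional identity before them.
2. Add *Through my work* to the source question.
3. List the employment item as a predictor in section 6.3.
4. Report measures (a)-(f) overall and, as a sensitivity analysis, with current staff excluded. Do not relabel the second set as the public estimate.

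The cost is a few seconds per respondent, a small change to the questionnaire and one extra table. Appendix 3 links to a live survey, so anyone who answered before the change would have no data on the item. Results should state how many that is and acknowledge the limitation for them.

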4.2 Informed Consent

Once logged onto the survey and having read the participant information sheet, informed consent will be obtained by a series of self-ticked boxes (See Appendix 2). These include confirmation/understanding on:

- Age
- How participants may withdraw at any time and what happens to any data given if they do

- That data given will be used for analysis and publication
- That participants will not be identified from the answers given
- That not everyone will see the same questions or definitions
- Whom to contact for questions or problems
- That they consent to take part in the survey

Only after all boxes have been ticked will the participant be able to commence the study (See Appendix 3).

It will not be possible for the study team to identify those taking part and therefore assess capacity for consent (nor monitor any fluctuations in capacity). However, as the study only involves filling in an online survey, no harm will be done to any of the participants who lack capacity, or who have fluctuations in capacity.

4.3 Study Assessments/Interventions

This is a single 20-25 minute survey. No interventions or treatments are scheduled

4.4 Definition of End of Study

The survey will close on the 31st May 2020 which will be defined as the end of the study. The survey will not be accessible after this date.

5. SAFETY REPORTING (IF APPLICABLE)

Not applicable.

6. STATISTICS

6.1 The Number of Participants

The study team aim for a power of 0.9 to detect three-group differences in quantitative variables with f = 0.1 (Cohen's "small" effect size), and therefore a total response rate of at least n = 1,269. Based on sites who have expressed interest, our total estimated sample size is 20,000.

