2.2 Secondary Objectives

a) To establish if opinions on sharing mental versus physical health data are affected by the "framing" of risk versus benefit, testing the hypothesis that a "security"-focused framing statement will increase reluctance to share mental (versus physical) health data regardless of purpose and a "holistic" framing statement will have the opposite effect.

b) To propose a design of a national consent form governing NHS data sharing and seek views on it.

c) To seek public views on a national web portal to sign up for mental health research.

d) To examine views on "trusted third party" linkage followed by de-identification for research, between health data and a range of other UK state-held information sources.

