6.2 Sampling

Study participants will be members of the public from the UK who wish to take part in the online survey. REDCap will be used to ensure balanced randomisation to the framing statements.

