6.3 Analysis of Endpoints

The study team will collect data on people's preferences regarding data sharing using Likertstyle scales, yielding interval/ordinal data on preferences (e.g. "very unlikely to share"/"strongly disagree" through to "very likely to share"). For part of the survey, the team will superimpose a randomised intervention, namely a framing statement, prior to seeking views relating to the sharing of mental versus physical health data. The framing statement will be one of three: a "security" framing emphasising previous work reporting others' greater concerns about sharing mental health data versus other kinds of health data; a "neutral" statement; and a "holistic" framing emphasising the interrelationship between mental and physical illness.

The team will examine the distribution of response data and anticipate using general linear modelling when its assumptions are satisfied (e.g. normally distributed residuals) ²⁸ but non-parametric alternatives (e.g. Kruskall-Wallis H test) where they are not. They will use R ²⁶ for statistical analysis. Predictors to be examined include age range, gender, ethnicity, self-reported educational level, geographical indicators (NHS region of respondent, index of multiple deprivation), personal experience of relevant NHS services/disorders, and experimental manipulation (framing).

Primary measures will be the self-reported overall degree of support for: (a) sharing physical health data for NHS clinical care without explicit consent each time, and how far such sharing should extend; (b) likewise for mental health data; (c) sharing de-identified structured physical health data for research without explicit consent, and how far such sharing should extend (e.g. NHS, academic, charities, industry, publicly); (d) likewise for mental health data; (e) as for (c) but with de-identified free text data; (f) as for (d) but with de-identified free text data.

Secondary measures will include (g) the effect of the framing interventions; (h) the degree of support for a single national sign-up mechanism for sharing one's health data for clinical care

and/or research; (i) views on a prototype national NHS data sharing consent form; (j) views on trusted-third-party linkage between health data and a range of other UK state-held data sources (e.g. education, criminal justice).

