We would like to know/gauge your understanding of how NHS clinical care providers currently share your identifiable health data for your clinical care, without asking you each time. If you are not sure, please have a 'best guess' as to what you think might happen.

My understanding is that (please tick only one):

- My identifiable health data is currently shared freely between all NHS sites across the UK-i.e. all acute hospital Trusts, my GP, all mental health Trusts, ambulance service etc. in the whole UK
- My identifiable health data is currently shared between all NHS sites but only in the home nation that I live in -- i.e. shared only in England, or Scotland, or Northern Ireland, or Wales, but not between them
- My identifiable health data is currently only shared between all NHS sites in my region (cluster of hospitals nearest to your local hospital)
- My identifiable health data is currently only shared between my GP, acute local hospital, local mental health Trust and other local services
- My identifiable health data is currently not shared between any NHS sites

Q2.

MOST hospital Trusts, GPs, mental health Trusts are separate and currently DO NOT share identifiable health data without asking you, though they correspond and communicate with each other with your permission.

In view of the statement above, we would now like to ask you your views on sharing your own identifiable health data for YOUR CLINICAL CARE, without having to be asked each time (please tick only one):

- I would like my identifiable health data to be shared for clinical purposes with any part of the NHS in the UK, without asking me first
- I would like my identifiable health data to be shared for clinical purposes with any part of the NHS in my home nation only (i.e. only in England, or only in Northern Ireland, or only in Scotland, or only in Wales) without asking me first
- I would like my identifiable health data to be shared for clinical purposes with any part of my region (cluster of hospitals nearest to your local hospital), without asking me first
- I would like my identifiable health data to be shared for clinical purposes only with my GP, local hospital, and local mental health services, without asking me first
- No one in the NHS should share my identifiable health data without asking me first
- Not sure

We would now like to ask you some questions about your own PHYSICAL and MENTAL health. You can 'prefer not to say' if you wish.

Q3

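### The minimum of 1,269 is right for a non-directional three-group test, but the framing hypothesis is ordered and directional, and neither 6.1 nor 6.3 names a contrast that tests it

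*Protocol*

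**What the plan says.** Section 6.1 gives the basis for the minimum: "The study team aim for a power of 0.9 to detect three-group differences in quantitative variables with f = 0.1", "therefore a total response rate of at least n = 1,269". It gives no alpha, no sidedness and no pattern for the three means. Its next sentence reads: "Based on sites who have expressed interest, our total estimated sample size is 20,000".

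The only three-group structure in the protocol is the framing randomisation. Section 6.2 says "REDCap will be used to ensure balanced randomisation to the framing statements", and section 6.3 describes the arms as security, neutral and holistic.

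Section 2.2(a) gives the hypothesis for these arms. The security statement is expected to increase reluctance to share mental (versus physical) data, whatever the purpose, and the holistic "framing statement will have the opposite effect".

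For analysis, 6.3 anticipates general linear modelling with framing among the predictors, or a non-parametric alternative such as Kruskal-Wallis. It names no directional contrast and lists the framing effect as a secondary measure (g), although 2.3 includes it in the principal outcome.

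**The concern.** The power statement and the hypothesis are both in the protocol, and they refer to different questions. A significant omnibus F or Kruskal-Wallis test says that the three arms are not all alike. It does not say that security lies below neutral, that holistic lies above it, or even that the extremes fall in the predicted order. That gap is present at any sample size.

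Two things are at stake. If no contrast is fixed in advance, the direction will be read from pairwise comparisons chosen after the data are seen. And a reader of 6.1 may take 0.9 at 1,269 as the power for showing that each framing moves opinion, which it is not.

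**Working it through.** **Inputs from the protocol.** Power 0.9, three groups, f = 0.1, minimum N = 1,269, expected N = 20,000 (6.1); balanced allocation (6.2), read as 1:1:1, so 423 per arm at the minimum.

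**Assumed, because not stated.** Alpha 0.05; the pattern of the three means, with equal spacing as the base case and other spacings as the range.

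**1. The plan's own figure.** Omnibus F test, degrees of freedom 2 and N - 3, noncentrality N × f². At N = 1,269 the noncentrality is 1,269 × 0.01 = 12.69, and power at alpha 0.05 is 0.9001. This is the smallest N reaching 0.9. Searching in equal arms, other alphas do not reproduce it: 0.10 gives 1,050, 0.025 gives 1,482 and 0.01 gives 1,749. So 1,269 is the omnibus size at 0.05.

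**2. Differences implied by f = 0.1.** With means at -d, 0, +d in SD units, f = d × √(2/3), so d = 0.1 × √1.5 = 0.1225 for each framing versus neutral and 2d = 0.245 for holistic versus security.

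**3. Power at 423 per arm.** The standard error of a difference between two arms is √(2/423) = 0.0688 SD.

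- Ordered contrast (-1, 0, +1), which with equal arms is holistic minus security: 0.245 / 0.0688 = 3.56, power 0.945 two-sided. It reaches 0.9 at 351 per arm, 1,053 in total.
- Each framing versus neutral: 0.1225 / 0.0688 = 1.78, power 0.43 at two-sided 0.05, 0.55 at one-sided 0.05.
- Both comparisons with neutral significant at two-sided 0.05 (their estimates correlate at -0.5): about 0.10.

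**4. Unequal spacing, same f, two-sided 0.05, 423 per arm.** The position of neutral is its distance from the nearer framing as a share of the distance between the two framings.

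| Position of neutral | Smaller difference vs neutral | Larger difference vs neutral | Ordered contrast |
|---|---|---|---|
| midway | 0.43 | 0.43 | 0.945 |
| two-fifths | 0.29 | 0.56 | 0.94 |
| one-third | 0.21 | 0.64 | 0.94 |
| one-quarter | 0.14 | 0.73 | 0.93 |

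The ordered contrast barely depends on spacing. The comparisons with neutral depend on it heavily.

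**5. Size for 0.9 on each comparison with neutral, equal spacing.** Two-sided 0.05: 1,402 per arm, 4,206 in total (4,203 by the normal approximation). One-sided 0.05: 3,426 by the normal approximation. At 4,206, power for both together is about 0.80.

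**6. At the expected 20,000** (about 6,667 per arm), each comparison with neutral has power above 0.9999 under equal spacing. With neutral at one-third the smaller difference (0.080 SD, standard error √(2/6,667) = 0.0173, ratio 4.63) still has about 0.996. At one-quarter (0.059 SD, ratio 3.40) it has about 0.92.

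**The case against.** Section 6.1 claims 0.9 only for three-group differences, and that claim is exactly right. This stands: nothing in 6.1 is miscalculated.

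A reader might infer that the framing hypothesis has only 43% power. The documents do not support that. Section 2.2(a) does not mention a comparison with neutral, so one ordered contrast is as fair a reading as two separate comparisons, and that contrast exceeds the 0.9 target at 1,269. The 43% also requires equal spacing and two-sided 0.05, neither of which the protocol states, and it applies only near the minimum, whereas 6.1 expects 20,000.

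A general linear model with framing as a predictor allows planned contrasts, and contrast detail is often left to the SAP, which is not shown. This stands in part. It rules out saying that the plan cannot test its hypothesis. It does not remove the mismatch between the hypothesis in 2.2(a) and the test for which 6.1 justifies its minimum.

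The ordered contrast has a limit of its own: with equal arms the neutral mean has zero weight, so it shows direction between the extremes but not which arm moved. That stands, and it is why the comparisons with neutral must follow.

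Survey question Q2 in Appendix 3 ("we would now like to ask you your views on sharing your own identifiable health data for YOUR CLINICAL CARE") comes before randomisation and is not among the predictors in 6.3. A reader might infer that adjusting for it would sharpen the framing test appreciably. The documents give no basis for that: it is a single-choice item on geographical scope for clinical sharing, with a Not sure option and no split between mental and physical data. Leaving it out is not an error.

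**Conclusion.** The point holds as a mismatch between the sample-size statement and the hypothesis, not as an arithmetic error or a shortage of respondents. The minimum is justified for an omnibus test that is silent on direction, and neither 6.1 nor 6.3 names the contrast that 2.2(a) calls for.

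The ordered contrast is well powered at the minimum whichever of the spacings above applies. What 1,269 does not secure is evidence on each framing against neutral. The sizes given rest on f = 0.1, equal arms and an inferred alpha of 0.05; the figures for comparisons with neutral rest also on the spacing and sidedness shown. The power shortfall would matter only if recruitment ended below about 4,200, roughly a fifth of the expected 20,000 (4,206 / 20,000 = 0.21). The lack of a named directional test matters at any size. As framing is a secondary measure, this is a change that should be made, not one on which the study depends.

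**What to change.** In 6.3, name the ordered contrast (security -1, neutral 0, holistic +1) on mental-minus-physical willingness to share as the test of objective (a). Follow it in fixed order with security versus neutral and then holistic versus neutral, each tested only if the step before it is significant, so that three tests do not inflate the error rate. If the linear-model assumptions fail, use a rank test for ordered groups (such as Jonckheere-Terpstra) in place of Kruskal-Wallis for the ordered step.

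In 6.1, state the alpha and sidedness, and say that 1,269 is the omnibus size. Add that it gives about 0.945 for the ordered contrast but, with equally spaced means, only about 0.43 (two-sided 0.05) or 0.55 (one-sided 0.05) for each framing versus neutral, and about 0.21 and 0.64 (two-sided) with neutral one-third of the way. Add that about 4,200 in total gives 0.9 for each under equal spacing, and that power is near 1 at the expected 20,000.

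Optionally, add pre-randomisation Q2 to the framing models as a categorical covariate, keeping Not sure as a category, without claiming a specific gain for the mental-minus-physical difference.

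The cost is wording in two sections. No extra respondents and no change to the survey are needed.
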